1. Allow refinement of clinical and physiological criteria for patient selection and refinement of protocols for the operative procedure and concomitant medical therapy and rehabilitation post-operatively – the results of the Feasibility Study will allow effective planning of a larger study to examine device efficacy
2. Develop predictors for adverse events and measures for minimizing the frequency and/or severity of such events
3. Determine the parameters of implantation, patient recovery, hospitalization, rehabilitation and home discharge
4. Determine the means to design a successful pivotal trial in regards to the anticipated randomization, feasibility of blinding, core lab procedures and data collection

PATIENT SELECTION

Inclusion Criteria

Patients of both genders who satisfy all inclusion and exclusion criteria are eligible for this clinical study. Patients must meet the following criteria:

1. Patient has ACC/AHA Stage C heart failure and remains in NYHA Class III - ambulatory Class IV despite optimal **medical** therapy. Patients must have stable, evidence-based optimal medical therapy for heart failure as defined below:
 - ACE inhibitor or ARB (Angiotensin Receptor Blocks) at least 30 days preceding implant or nitrate/hydralazine at the investigators discretion
 - Beta-blocker for at least 90 days and stable for 30 days preceding implant
Note: Stable is defined as no more than a 50% reduction or 100% increase in the medications listed above. Transition within a therapeutic class is allowed if the dose is equivalent.
2. Patient has left ventricular ejection fraction (LVEF) $\leq 35\%$
3. Patient has had Cardiac Resynchronization Therapy (CRT) for at least 90 days prior to enrollment or is not indicated for a CRT device
4. Patient has had an implanted cardio-defibrillator (ICD) at least 30 days prior to enrollment or is not indicated for ICD implantation.
5. Patient is at least 18 years of age and not older than 75 years
6. Patient six minute hall walk assessment between 100–350 meters
7. Patient understands the nature of the procedure, is willing to comply with associated follow-up evaluations, and provide written informed consent prior to the procedure

Exclusion Criteria

Candidates must be excluded from the study if any of the following are met:

1. Patient has any evidence of:
 - Ascending aortic calcification on posterior–anterior or lateral chest x-ray at initial screening
OR

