The patient must perform a six–minute hall walk test (6MHW) at Baseline, and at 1, 3, 6, 12, 18 month visits and annually thereafter with the C-Pulse™. Detailed information is included in Appendix P.

A familiarization test is required, but may have been performed in the previous one–year prior to implant. Instructions for conducting a six-minute walk test are located in Appendix P.

Data will be completed on the Baseline and follow-up eCRFs.

Quality of Life Assessment - (Baseline, 1, 3, 6, 12, 18 month and annual follow-up visits)

The patient must complete the Minnesota Living with Heart Failure Questionnaire (MLWHF) and the Kansas City Questionnaire (KCCQ) at Baseline, 1, 3, 6, 12, 18 month and annual visits.

Copies of the questionnaires are included for reference in Appendix N.

Data will be completed on the Baseline and Follow-up eCRFs.

Fatigue Impact Scales - (Baseline, Pre-Discharge, 1, 3, 6, 12, 18 month and annual follow-up visits)

The patient must complete the Fatigue Impact Scale and the Daily Fatigue Impact Scale at Baseline, Pre-Discharge, 1, 3, 6, 12, 18 month and annual visits.

Data will be completed on the Fatigue Impact and Daily Fatigue Impact eCRFs.

NYHA Class Assessment - (Baseline, 1, 3, 6, 12, 18 month and annual follow-up visits)

A clinician at each site shall complete the NYHA Classification at Baseline, 1, 3 6, 12, 18 month and annual visits.

Data will be completed on the Baseline and follow-up eCRFs. Refer to Appendix O for detailed description of the assessment.

Concomitant Medications (Baseline, 1, 3, 6, 12, 18 month and annual follow-up visits)

All medications will be recorded on the Medication eCRF. Doses are required for all cardiac medications including diuretics. Heart Failure medications such as ACE inhibitors and Beta Blockers must remain stable through the six month study period. Upward titration is not permitted beyond the baseline equivalent dose.

Cardiopulmonary (CPX) Testing - (Baseline and 6 month follow-up visits)

Two CPX tests may be required pre-operatively:

- 1) a familiarization test to allow the patient to become familiar with walking on a treadmill and with the breathing apparatus in his/her mouth and
- 2) a baseline test.

During the familiarization, the patient should exercise to his/her symptomatic maximum. If the patient reaches his/her maximum, this test will be considered the baseline test.

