8. Blood sugars: An Insulin infusion, titrated to Q1–4hr blood sugar measurement will be established in patients with diabetes or other glucose intolerance until a regular diet and normal diabetic therapy can be re-introduced.
9. Active deep vein thrombosis management includes TED stockings, subcutaneous Clexane or similar and bed leg exercises.
10. Early mobilization and graduated physiotherapy is to be conducted as tolerated from day 1, but the driver should not be used in a wearable configuration in the first week or until the chest incision is stable and comfortable. Use of the driver with the vest should be gradually built up and used with assistance from physiotherapy or other hospital staff.
11. The C-Pulse® can be de-activated intermittently for patients that are considered symptomatically stable per physician discretion (e.g. acceptable degree of shortness of breath and absence of dizziness), initially for short intervals (less than 5 minutes) once or twice a day, and this may be built up after 7–10 days post-operatively such that de-activation periods provide an opportunity for the patient to be free of the Driver for 15 minute intervals during the day or night. The Driver should not be ‘Off’ for greater than 30 minutes at any one time and not be ‘Off’ for a maximum of four hours total per day. **For the extent of the trial, the device should be used at least 20 hours per day (i.e. device must be used greater than 80% of the time).**
12. Heart failure medications should be re-started cautiously and drug doses titrated to clinical effect. It is recommended that the following regime be used as a guideline for post-operative medications:
 - Dopamine or Dobutamine for first 1–7 days, weaned down
 - Diuretics at pre-op dose or higher (including IV infusion as required) from day 1: Diuretics may be weaned as indicated later in the post-operative period
 - ACE inhibitors from day 2–3 – aim to titrate to then maintain at pre-op dose for duration of the study follow-up
 - Beta blocker from day 5–7, as tolerated – aim to titrate to then maintain at pre-op dose for duration of the study follow-up
13. Strict hygiene/hand washing must be practiced for all staff handling patient and lines. Remove all indwelling catheters as soon as possible. Change other lines regularly (at least every 4–7 days) as per hospital policy.

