Safety will be represented in the composite device-related adverse event rate which will be reported with its 95% two-sided exact confidence interval. The composite device-related adverse event rate will be assumed to follow the Binomial Distribution. The DSMB will decide the clinical acceptability of this observed event rate in assessing trial success.

Additionally each event will be presented with its respective rate and confidence interval. Death will be separated into deaths that occur before 30-days post-procedure and those that occur between 30-days post-procedure and 6 months.

Efficacy measurements

The efficacy of C-Pulse® will be evaluated by assessing the change of the efficacy variables from baseline to 6 months post-implant. The following measurements will be taken at baseline and 6-months.

- Peak VO₂
- Quality of Life as measured by the Minnesota Living with Heart Failure (MLWHF)
- HF Symptoms as measured by NYHA
- Six Minute Hall Walk Test

Performance Requirement

Trial success will be evaluated by analyzing each patient's response to the four efficacy variables. A responder analysis will be performed for each patient assessing the response to each of the four efficacy variables. Each efficacy variable will be assessed for clinical improvement ("responder"), decline ("non-responder") or no change ("indeterminant").

Clinical improvement will be defined for each efficacy variable as:

- 1.2 ml/kg/min improvement in peak VO₂
- 7 point improvement in MLWHF score
- 1 class improvement in NYHA
- 50 meter improvement in the Six Minute Hall Walk

Clinical decline will be defined for each efficacy variable as:

- 1.2 ml/kg/min decrease in peak VO₂
- 7 point decrease in MLWHF score
- 1 class decrease in NYHA
- 50 meter decrease in the Six Minute Hall Walk

A patient that shows no improvement or decline in a particular endpoint will be labeled as "indeterminate" for that endpoint.

The overall percentage of responders, non-responders and indeterminates for each efficacy variable along with the respective 95% two-sided exact confidence interval will be presented. Additionally the point estimate for the average change and its respective standard deviation will be presented for peak VO₂, MLWHF, and the Six Minute Hall Walk. The improvement in NYHA will be presented by a cross-tabulation summary. The DSMB will decide the clinical acceptability of this responder analysis in assessing trial success.

Secondary Objectives

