The secondary objectives are descriptive in nature and will be evaluated in order to gain additional information regarding the C-Pulse® system. There are no specified performance criteria for these objectives. For continuous measures the mean, standard deviation, minimum and maximum values will be presented. For categorical variables the frequency and percent will be presented.

Endpoints consistent with the primary safety and efficacy objectives will be evaluated at all additional time points.

1. The adverse event rate will be presented at 3, 6, 12 and 18 months post-procedure, and annually for years 2-5 post-procedure.
2. The change from baseline to follow-up will be evaluated for peak VO₂, Six Minute Hall Walk, MLWHF, Fatigue Impact Scales and heart failure symptoms from NYHA.

The device failure rate will be quantified. Failure will be defined as both failure of the device, and failure of the device to be programmed to the treatment.

Additionally, the adverse event rate for each of the adverse events described in the Adverse Event Definitions section – pages 36-40 – will be provided. Exact 95% two-sided confidence intervals with an underlying Binomial Distribution will be provided for each event. Adverse events will also be tabulated by attribution (seriousness, device-relatedness, and procedure-relatedness) according to the CEC.

The following additional efficacy measures will be analyzed at each time point to evaluate the efficacy of the C-Pulse® System. For these measures the averages and the average change from baseline to each follow-up period will be presented along with the trend over time:

- Hemodynamic measures are from right heart catheterization (RHC): Cardiac Index (CI), Pulmonary Artery Pressure (PAP), Pulmonary Capillary Wedge Pressure (PCWP), and Cardiac Output (CO).
- Quality of Life
 - Kansas City Questionnaire.
- Blood tests (e.g. Serum sodium, serum creatinine, serum bilirubin, hemoglobin, ALT and AST).
- Concomitant cardiovascular medications

The following measures will also be summarized:

- Re-hospitalization (HF-related and all-cause)
- Duration of support/survival duration.
- Length of time to ICU and hospital discharge
- Device evaluation – Device log and C-Pulse® User log will be evaluated and summarized. Average daily device use will be provided for each time period.

Sample Size Determination

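### Averaging concomitant cardiovascular medications gives no interpretable summary, and no planned table sets drug change beside the responder result

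*Combined protocol and SAP*

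**What the plan says.** Statistical Methods and Data Analysis, Secondary Objectives, lists additional efficacy measures: right-heart hemodynamics, the Kansas City questionnaire, blood tests and, last, "Concomitant cardiovascular medications". One rule introduces the whole list: "For these measures the averages and the average change from baseline to each follow-up period will be presented along with the trend over time". No class, unit, dose-equivalence scale or derived variable is given for medications. The same section opens with general rules: continuous measures get mean, standard deviation, minimum and maximum, and "For categorical variables the frequency and percent will be presented".

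The Performance Requirement under Efficacy measurements says "A responder analysis will be performed for each patient assessing the response to each of the four efficacy variables". Results are percentages with exact 95% confidence intervals, and the DSMB decides their clinical acceptability. Medication does not enter this analysis as a condition, a stratum or a sensitivity analysis.

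On drug use itself, Summary of Required Testing, Concomitant Medications, states "Doses are required for all cardiac medications including diuretics". It also requires drugs such as ACE inhibitors and beta-blockers to stay stable for six months and bars increases beyond the baseline equivalent dose. The Protocol Deviations section lists, among things that are not deviations, upward titration above 100% of the initial dose and the addition of an ACE inhibitor or ARB after implant.

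**The concern.** Cardiac index, a questionnaire score and serum sodium each have one unit, so a mean change is meaningful. A medication list has none. Different agents have different dose scales, and an average over them depends on the mix of agents and on the scale chosen. Two analysts could not be expected to produce the same table from this text.

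The table matters because the study is open-label with one arm. Change in heart-failure drugs is one rival explanation for gains in peak VO₂, MLWHF, NYHA class and walk distance. The DSMB judges success from the responder analysis, and Sample Size Determination says that estimates from this study will be used to power the pivotal study. Those readers would not see, from the planned output, how many responders also had a drug started or increased. The deviation log may not show it either, because of the exemptions in Protocol Deviations.

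**Working it through.** The plan states no figure on this point, so there is none to reproduce. The check compares the sections and then uses illustrations. All doses and response rates below are assumed.

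**Sections side by side**

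- Concomitant Medications: stable for six months, with no increase beyond the baseline equivalent dose.
- Protocol Deviations: titration above 100% of the initial dose is not a deviation. Whether this means any dose above the initial one or an increase of more than 100%, it exempts doses above baseline. Adding an ACE inhibitor or ARB is also exempt.
- Result: a change that the first section bars need not be logged under the second. It would still be on the Medication eCRF, so the medication summary is the main planned output in which to see it.

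**What an average change can show**

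Mean change = sum of (follow-up dose − baseline dose) / number of patients.

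- Cancellation: 20 patients at 100 units; 5 double, 5 stay, 10 halve. (5 × 100 + 5 × 0 − 10 × 50) / 20 = 0, although 15 of 20 changed.
- Mixed scales: 10 patients go from 6.25 to 12.5 mg and 10 from 100 to 75 mg. Mean change = (10 × 6.25 − 10 × 25) / 20 = −9.375 mg. Mean percent change = (10 × 100% − 10 × 25%) / 20 = +37.5%. The sign depends on the scale.
- Equivalent switch: all at 20 units, one patient moved to an assumed equivalent 160 units of another agent. With 20 patients the mean rises (160 − 20) / 20 = 7 units, or 7 / 20 = 35%. With 40 patients, 140 / 40 = 3.5 units, or 17.5%. Therapy is unchanged in both cases.

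**What a link to response could show**

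Assume that half the patients respond on one efficacy variable. Keep every patient in the denominator n, and do not count as responders those with a drug started or increased. With x remaining responders, the exact 95% limits are the 0.025 quantile of Beta(x, n − x + 1) and the 0.975 quantile of Beta(x + 1, n − x). Sample Size Determination gives n = 20; Study Size and Duration gives n = 40 after the expansion.

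| Share of responders not counted | n = 20 | n = 40 |
|---|---|---|
| none | 10: 50% (27.2 to 72.8) | 20: 50% (33.8 to 66.2) |
| one fifth | 8: 40% (19.1 to 63.9) | 16: 40% (24.9 to 56.7) |
| two fifths | 6: 30% (11.9 to 54.3) | 12: 30% (16.6 to 46.5) |
| one half | 5: 25% (8.7 to 49.1) | 10: 25% (12.7 to 41.2) |

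**The case against.** The strongest reply has four parts.

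- **Restriction by design.** The Concomitant Medications section limits intensification before the 6-month endpoint, and the post-implant guidance aims to return ACE inhibitors and beta-blockers to the pre-operative dose. This stands, so the documents do not show that drug change is the leading explanation for any response. It is weakened by the exemptions in Protocol Deviations.
- **General rules.** Minimum and maximum would be shown for continuous measures: −50 and +100 in the cancellation example, +140 as the maximum in the switch example. Categorical measures would get counts. This softens the masking. But the plan does not say that medications are categorical, it puts them under the averaging rule, and a range does not count the patients who changed or connect them with response.
- **Borrowed text.** "Transition within a therapeutic class is allowed if the dose is equivalent" belongs to the eligibility definition of stable therapy before implant; it is not an analysis rule. "Diuretics may be weaned as indicated later in the post-operative period" comes from guidance headed as prior to discharge, and weaning is not intensification. Both limits stand. The text shows only that equivalent switches and diuretic changes are foreseen.
- **Weight.** "The secondary objectives are descriptive in nature and will be evaluated in order to gain additional information regarding the C-Pulse® system", and the study is not powered for significance. This stands and keeps the point modest.

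A reader might infer that the averaging rule leaves the trial unable to tell whether responders improved on the device or on changed drugs. The documents do not support that. Doses are recorded per patient, so the missing table can be made from data already collected. And no medication table could attribute benefit to the device in a single-arm study.

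**Conclusion.** The point holds in a limited form. As written, the medication summary has no defined meaning across agents, and the planned output does not set drug change beside the responder result. The conflict between Concomitant Medications and Protocol Deviations means that the deviation log cannot be relied on to fill that gap. The sponsor must reconcile those sections; this review takes no position on which rule is right.

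The size for this trial cannot be derived, because the documents give no doses, no frequency of drug change and no expected response rate. The illustrations show that a mean change of 0 is compatible with change in 15 of 20 patients. They also show that a 50% response would fall by 10 to 25 percentage points if a fifth to a half of the responders had intensified drugs. With 20 to 40 patients the intervals are wide, so the result would be descriptive. The defect is worth correcting because the cost is small and the responder analysis decides trial success.

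**What to change.** - In Secondary Objectives, take medications out of the averaging rule. For each class (ACE inhibitor/ARB, beta-blocker, diuretic, other heart-failure drug), report the number and percent of patients with a drug started, increased, unchanged, decreased or stopped at 1, 3 and 6 months, relative to their own baseline-equivalent dose. Table 3 already collects medications at these visits.
- For each of the four efficacy variables, add one table of responder, indeterminate and non-responder by any heart-failure drug started or increased by 6 months (yes/no). That is 3 × 2 = 6 cells per table. Crossing four classes with four variables would give 16 tables of 5 × 3 = 15 cells, too sparse for 20 to 40 patients.
- Add a sensitivity responder percentage with exact 95% confidence interval. Keep all patients in the denominator and do not count as responders those with a drug started or increased. Do not simply drop the intensified patients: that conditions on a post-implant event and can inflate response by removing those who worsened and were given more drug.
- Reconcile Concomitant Medications with Protocol Deviations on upward titration and added drugs.

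Cost: a dose-equivalence convention must be fixed in advance (the protocol already relies on the idea of an equivalent dose), a few tables are added, and the sensitivity percentage may look less favourable. No new data are needed.

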This feasibility study intends to examine the effect of C-Pulse® on long-term heart failure, and to look for trends in performance indicators. This study is not powered to detect statistical significance. As such, clinical judgment is required to assess device safety and potential efficacy from data collected during this study. This clinical judgment will be provided by the DSMB.

Justification of Methodology

This study is designed as an open-label single-arm study to develop a further understanding of the C-Pulse®. It will provide safety and efficacy information for patients in whom C-Pulse® is implanted and maintain counterpulsation for six months or longer.

At six months post-procedure, the patients will provide an adverse event profile related to surgical placement of the C-Pulse® and six months employment of C-Pulse® counterpulsation. After six months of the study there will be additional information related to the adverse event profile. The patients will provide an adverse event profile for patients in whom C-Pulse® is placed and maintain counterpulsation for greater than six months.

Similarly, these patients will provide an efficacy profile. At six months post-procedure, the patients will provide information on how well a patient improves since baseline through six months of counterpulsation. After six months these patients provide additional efficacy information related to how well a patient improves since baseline through greater than six months of counterpulsation.

Primary Safety Measures

The safety of the C-Pulse® will be evaluated by reviewing a composite of the device-related adverse events through six months, as classified by the CEC. The composite device-related adverse event rate will be the percent of patients who experience at least one of the following adverse events as adjudicated by the CEC as device-related out of the total number of patients:

- Death
- Neurological Dysfunction
- Aortic Disruption
- Myocardial Infarction
- Major Infection
- Any other device-related adverse event (as adjudicated by the CEC)

The definitions for these adverse events are provided in the Adverse Event Definitions section.

Performance Requirements

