This is a single-arm study designed to determine the safety of the C-Pulse® as well as give an insight into the efficacy of counterpulsation.

Because estimates from this study will be used to power the pivotal study, this study must be able to provide such estimates. A sample size of 20 implanted patients is considered clinically sufficient to give indications of both safety and potential efficacy. With this sample size, we feel we can decide whether to proceed to a pivotal study, determine endpoints for such a study, and design the study to answer the proposed hypotheses. Up to approximately 10 additional subjects may be enrolled to account for subjects who do not meet inclusion/exclusion criteria involving non-standard clinical practices.

Subjects for Analysis

Patients will be included in two analyses. The primary analysis will be an “as- treated” analysis, wherein only subjects in whom the device is placed are analyzed. The secondary analysis will be an “intention to treat” analysis, wherein all followed-up subjects will be analyzed.

RISK ANALYSIS

SHC has evaluated the potential risks and benefits (listed below) associated with the C-Pulse® and its appropriateness for therapy for symptomatic Stage C HF patients with NYHA Class III–ambulatory Class IV symptoms. Evaluation is based on the preclinical and clinical experiences to date. The adverse event definitions in the previous sections highlight and expose a standard level of expected risks. Any unanticipated risks and associated events will be captured through the adverse event reporting.

Potential Risks

Risks Related to the Implantation Procedure

Surgical risks along with mitigations specific to the C-Pulse® system include:

- Damage to Cuff on implantation not detected
- Misplacement of ECG lead – not able to sense ‘R’ wave appropriately

Implantation is an invasive procedure requiring a median sternotomy and the use of general anesthesia and mechanical respiratory support. The potential risks associated with the implant procedure also include those associated with any cardiothoracic surgery, including implantation of devices and include the following:

- Bleeding
- Infection
- Neurological Dysfunction
- Renal Dysfunction
- Cardiac Arrhythmias
- Pericardial Fluid Collection
- Aortic disruption
- Device Malfunction
- Hemolysis
- Hepatic Dysfunction
- Hypertension
- Myocardial Infarction
- Psychiatric Episode
- Respiratory Failure
- Right Heart Failure
- Arterial Non–CNS Thromboembolism

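### The Sample Size Determination section still describes 20 implanted plus about 10 more enrolled, although the study now allows 40 implanted of about 60 consented, and no text fixes which cohort the primary 6-month analyses use

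*Combined protocol and SAP*

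**What the plan says.** **Sample Size Determination** (Statistical Methods and Data Analysis) gives the size as follows: "A sample size of 20 implanted patients is considered clinically sufficient to give indications of both safety and potential efficacy". It rests the next step on that number, "With this sample size, we feel we can decide whether to proceed to a pivotal study", and gives the purpose as planning the pivotal trial: "Because estimates from this study will be used to power the pivotal study, this study must be able to provide such estimates". On enrolment it adds: "Up to approximately 10 additional subjects may be enrolled to account for subjects who do not meet inclusion/exclusion criteria involving non-standard clinical practices". It does not mention the expansion.

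**Current design text** gives larger numbers:
- Study Size and Duration names 20 implanted patients as the primary population. It then allows 40 implants under the expansion, and up to about 60 consented.
- Design expands the population to 40 implanted, but ties the 6-month period before the pivotal trial to the initial 20.
- Appendix R has 20 expanded to a total of 40 in its Study Objectives and Study Design rows, and up to 40 implanted in its subjects row.

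**Analysis text** names no cohort:
- Under Subjects for Analysis, the primary as-treated analysis is one "wherein only subjects in whom the device is placed are analyzed".
- The safety composite counts patients with an event adjudicated as "device-related out of the total number of patients".
- Performance Requirements says of the composite: "The DSMB will decide the clinical acceptability of this observed event rate in assessing trial success".
- For peak VO2, the Minnesota score and the six-minute walk, "the point estimate for the average change and its respective standard deviation will be presented".

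**The concern.** A sample size section should describe the study that is being run. Here it describes a study half the size of the one in the design sections, and the analysis text does not say which of the two sizes applies to the primary 6-month results.

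This matters because the study has no numerical success threshold. The DSMB judges success from the observed composite rate and the responder percentages with their intervals, and the study's estimates are to be used to power the pivotal trial. Those figures differ according to whether they come from the first 20 patients or from everyone implanted. The study is open-label and the expansion follows the first 20, so a cohort left open could be settled after the early results are known.

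**Working it through.** **1. The plan's own figure.** No formula leads to 20. The section gives no alpha, power, effect size, standard deviation, event rate or target interval width, so there is nothing to reproduce. Only the counts can be compared.

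| Source | Implanted | Enrolled/consented |
|---|---|---|
| Sample Size Determination | 20 | 20 + 10 = about 30 |
| Study Size and Duration (expansion) | 40 | about 60 |
| Design | 40 | – |
| Appendix R, Study Design row | 40 in total | – |
| Appendix R, subjects row | up to 40 | – |

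Study Size and Duration counts a patient as enrolled once consent is signed, so about 30 and about 60 measure the same thing and cannot both be the plan. The implanted share is the same in both: 20/30 = 40/60 = 2/3. That pattern fits a section left as it was when both numbers doubled. All of these statements are in current text; none is taken from the revision history.

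**2. Which cohort the 6-month analyses use.**

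| Points to the initial 20 | Includes all implanted (up to 40), or sets no limit |
|---|---|
| Study Size and Duration: 20 as the primary population | Subjects for Analysis: as-treated set is everyone who has the device placed |
| Appendix R, Study Design: same | Primary Safety Measures: denominator is all patients |
| Design: 6-month period for the initial 20 | Efficacy Performance Requirement: no cohort named |
| Sample Size Determination: 20 is sufficient | Study Size and Duration (closing part) and Appendix R, Study Design: 6-month pre-pivotal period given without limiting it to 20 |

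No section says whether the primary 6-month results use the first 20, all implanted, or both.

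**3. Size of the difference.** The method is the plan's two-sided exact 95% binomial interval. For x events in n patients:
- lower limit = 2.5% quantile of Beta(x, n−x+1), or 0 if x = 0
- upper limit = 97.5% quantile of Beta(x+1, n−x)
- for x = 0 the upper limit reduces to 1 − 0.025^(1/n): 1 − 0.025^(1/20) = 16.8% and 1 − 0.025^(1/40) = 8.8%

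The counts are illustrative, because the plan states no expected rates. Every implanted patient is assumed to have data.

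| Observed rate | N = 20 | N = 40 |
|---|---|---|
| 0% | 0/20: 0–16.8% | 0/40: 0–8.8% |
| 10% | 2/20: 1.2–31.7% | 4/40: 2.8–23.7% |
| 30% | 6/20: 11.9–54.3% | 12/40: 16.6–46.5% |
| 50% | 10/20: 27.2–72.8% | 20/40: 33.8–66.2% |

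At 50% the interval is 45.6 points wide with 20 patients and 32.4 points wide with 40.

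**The case against.** The best reply is that the documents describe two stages. Twenty patients are the primary population and support the pivotal decision; the expansion then adds up to 20 more. A number called sufficient is not contradicted by implanting more patients. The as-treated rule separates implanted from non-implanted patients and was probably not written to decide between initial and expansion patients. The safety denominator is generic wording, and neither passage states 40. The DSMB meets repeatedly, so looks at different numbers are foreseen.

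Much of this stands. A reader might infer that the documents flatly contradict themselves on the analysed N, or that the text cannot hold both numbers. They do not support that, because the two-stage reading is available. What the reply does not remove is that the analysis text never adopts that reading, and that about 30 enrolled conflicts with about 60 on any reading.

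A reader might also infer that the study's power or error rate is compromised. That does not follow: the Statistical Methods section says the study is not powered for significance, and it sets no test or threshold. It is also true that 40 patients estimate a standard deviation better than 20, and that a rate in 20 differs by chance from the rate in the 40 containing them. Neither fact changes a pre-specified decision, so the point does not rest on them.

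**Conclusion.** The point holds in two linked parts. First, the stated sample size is wrong for the current design: 20 implanted and about 30 enrolled, against up to 40 and up to about 60. Secondly, the primary 6-month cohort is undefined: 20 on some sections, up to 40 on the literal analysis rules.

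The consequence is what the DSMB sees and what feeds pivotal planning. With no events, for example, the data would exclude composite rates above 16.8% or above 8.8%, depending on the cohort. The intervals rest on assumed counts and complete data; the mismatch in the counts rests on no assumption. Either cohort would be defensible once named. This should be corrected, but it does not invalidate the design.

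**What to change.** **Whichever cohort is chosen:** in Sample Size Determination, give the planned size as up to 40 implanted of up to about 60 consented, in place of the allowance of about 10 additional subjects.

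**Then name one primary 6-month cohort:**
- *All implanted patients.* State the exact-interval precision at 40 (0/40: upper limit 8.8%; 20/40: 33.8–66.2%). Align Study Size and Duration, Design, and the Study Objectives and Study Design rows of Appendix R, so that none of them sets the first 20 apart as the primary group.
- *The initial 20.* State the precision at 20 (0/20: upper limit 16.8%; 10/20: 27.2–72.8%). Limit to these patients the primary as-treated set, the safety denominator in Primary Safety Measures, and the 6-month pre-pivotal assessment in Study Size and Duration and the Study Design row of Appendix R. Report all implanted patients as a separate supporting analysis.

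Label the example rates as illustrative. The cost is wording only: no extra patients, visits or data.
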